### **G. Payment, including a prorated plan for payment:**

Subjects will receive a one-time compensation of \$200 for participating in this study. They will be given a ClinCard which works like a debit card. At Visit 3, payment will be added to the card by computer. The money will be available within 1 business day. Subjects can use the ClinCard at an ATM or at a store. They will be given one card during the study. The KUMC Research Institute will be given their name, address, social security number, and title of this study to allow them to set you up in the ClinCard system. Study payments are taxable income. A form 1099 will be sent to the subject and the Internal Revenue Service if your payments are \$600 or more in a calendar year. The subjects' personal information will be kept on a secure computer. It will be removed from the computer after the study is over and the money on the card has been used. The information will not be shared with other businesses. It will be kept confidential.

### **IV. Data Collection and Protection**

**Data Management and Security:** Information from these tests will be entered into a research database. The PI and Co-I's together with the study coordinator will supervise the data acquisition. Data will be coded for confidentiality and only the PI, study coordinator, and statistician will have access to the code. Hard copies of study files are kept in a dedicated, locked cabinet in a badge-access area. Subject data will be coded prior to sending it to the statistician for statistical analyses.

**Sample / Specimen Collection:** Samples will be labeled with a data code, and blood and tissue samples will be labeled with this code and stored in a locked freezer in a badge-access area. Blood and tissue samples will be stored indefinitely.

#### **A. Tissue Banking Considerations: N/A**

**Procedures to protect subject confidentiality:** All outcome measure data will be direct entered onto custom developed electronic source document forms created in Research Electronic Data Capture (REDCap). REDCap is a secure, web-based application designed to support data capture for research studies, providing: 1) an intuitive interface for validated data entry; 2) audit trails for tracking data manipulation and export procedures; 3) automated export procedures for seamless data downloads to common statistical packages; and 4) procedures for importing data from external sources. REDCap on the KUMC campus sits on a HIPAA compliant, password protected server. The KU ADC has extensive experience building and maintaining REDCap databases, including those used for the preliminary data in this application. Confidentiality is strictly safeguarded by HIPAA-compliant standards.

#### **Quality Assurance / Monitoring**

The study team will perform biannual source data verification and self-assessment of records to ensure that data are accurate.

### **V. Data Analysis and Reporting**

#### **A. Statistical and Data Analysis:**

The primary statistical analyses for Aims 1-2 utilize paired, pre-, post- acute exercise measurements. As such, we will analyze the data using the two-sample, paired t-tests. This will contrast overall changes in

brain metabolism following acute exercise (i.e., pre- vs. post-exercise differences) and between the intensity groups (moderate vs. higher intensity). We will conduct residual analyses to assess the appropriateness of this methodology to evaluate assumptions of common variance, normally distributed errors, etc. In the event any of the measures do not conform to these foundational assumptions, the nonparametric analogs will be used instead, such as the Wilcoxon rank sum test of the within-subject pre- vs. post-exercise measures. These measures will follow the intent-to-treat principals. Though a randomized design, we will also construct exploratory analyses that incorporate other adjustments using ordinary least squares (OLS) regression on the change scores as the outcomes, also with residual analysis and modified approach if indicated. This will allow for model adjustment to further examine these relationships. One further relationship will involve combining the results of the AD and ND subjects in a single model as described in our Aims. We will use OLS in this context to test for interactions between AD and ND subjects with respect to the acute exercise response (moderate vs. higher intensity) for these pre-/post-exercise change score outcomes. Finally, we will model change score outcomes as functions of the various other change score measures. This approach will enable us to observe how changes in cerebral glucose metabolism are driven by acute-exercise influenced changes in circulating biomarkers. We will conduct similar residual analyses appropriate to the regression models utilized to ensure appropriate inferences are drawn. While descriptive and exploratory in nature, we anticipate that this approach will illuminate and/or confirm our pre-conceived metabolic processes that are related to the acute exercise response, and that it will help identify likely reasons for prior exercise trial successes and failures through mechanistic discovery. We believe this study fits perfectly within the study paradigm for PAR-18-877 by the NIA, which states that identifying precise cellular mechanisms will provide important therapeutic targets.

Sample size justification. We powered our study based upon our primary variable of interest, cerebral glucose metabolism. Based on previous literature [6], the cerebral metabolic rate of glucose following acute exercise at (70% VO2max) ( $3.18 \pm 0.68$ ) was significantly lower compared with that of resting controls ( $4.25 \pm 0.27$ ). This study produced an effect size of 2.07 based on the independent t test design. However, given the small sample size of that initial study, we conservatively use much lower effect sizes. A two sample paired t test design with an effect size of 1.25 and a sample size of 15 AD subjects allocated to high intensity and 15 AD subjects allocated to moderate exercise would yield an estimated power of 91% using a conservative estimated effect size of 1.25. Dropping down to less than half the effect size produced in the preliminary data to 1.00 still provides 75% power, and using a still conservative 1.50 for the effect size indicates >95% power. (Power calculations were produced by nQuery Advisor® 7.0, 1995-2007.) We plan to recruit the same number of elderly healthy patients in the study. Accounting for a possible 10% attrition rate over the course of the study visits, we propose a total sample size of 60 (30 subjects in each diagnosis group with 15 individuals assigned to moderate and higher intensity acute exercise) Thus, we anticipate recruiting the sample size of 66, which will provide over 90% power based on a conservative estimate of the effect size from the literature and the use of paired difference scores for the primary endpoint, which should reduce variation in the response.

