Accumulating evidence suggests that the exercise-related metabolite lactate is an understudied effector of brain health. Lactate is an essential fuel for neuronal function. [7, 8] It is supplied to neurons through glucose metabolism in nearby glia [9, 10] and from peripheral blood, since the brain is permeable to lactate. [11] A drop in cerebral glucose metabolism is a marker of AD [12]. Thus, supplying neurons directly with lactate for oxidation may supplement energy requirements in AD, as has been suggested with ketones. [13] Importantly, circulating lactate levels rise during exercise [14]. Repeated increases in systemic lactate (acute exercise response) may transiently spare glucose by providing an alternative fuel. With routine exercise, acute responses may elicit adaptations that facilitate the use of lactate beyond that which occurs during acute exercise and contribute to brain benefits observed during chronic exercise interventions. In younger populations, higher exercise intensity evokes a greater lactate response compared to lower intensities [5] and elicits cognitive benefit. [15] Characterizing the acute effects of exercise intensity will greatly inform the design of future trials. We will also characterize diagnostic differences in lactate use. Finally, because acute exercise affects a variety of signaling pathways beyond lactate, we will also characterize the acute exercise response of a selected group of exercise-related biomarkers. We will achieve these goals through the following aims:

**Aim 1:** Compare the effects of acute, moderate intensity and acute, higher intensity exercise on cerebral glucose metabolism in nondemented (ND) elderly and AD subjects. ND (n=30) and AD (n=30) subjects will undergo a single bout of moderate intensity (45-55% HRR) or higher intensity (65-75% HRR) exercise to assess the effect of exercise intensity on acute change in brain glucose metabolism (rest to exercise). We hypothesize that both moderate and high intensity exercise will elicit a drop in global brain glucose

metabolism compared to quiet rest, but that the effect will be greater with higher intensity vs. moderate intensity exercise, and greater in ND subjects than in AD subjects.

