**Resting Protocol (Visit 2 or 3 – counterbalanced between subjects)**

Participants will arrive for FDG PET after having fasted for a minimum of 8 hours and will have a catheter placed for IV administration of FDG. Draw 1 will be performed right before FDG bolus is administered. Subjects will begin resting and will receive a single IV bolus of FDG minutes into resting. Draw 2 will be taken after 5 minutes of rest. Draw 3 will be taken after 20 minutes of rest. The participant will be moved to the PET scanner at minute 25 and Draw 4 will be taken at 30 minutes. The scan will start immediately at minute 35. After the scan is complete a blood draw will be taken at minute 45 and a short cognitive performance test (NIH Toolbox Cognition Battery) will be performed. The final blood draw will be taken after the testing is complete, at approximately minute 75.

**Acute Exercise Protocol (Visit 2 or 3 – counterbalanced between subjects):** Participants will report to the scan room for the baseline blood draw. After mounting the bicycle, subjects will be asked to begin exercise (warm-up) 5 min before the injection of FDG. One minute prior to warm up, while the subject is resting and sitting on the bicycle, Draw 1 will be taken. At time T0 the subject will pedal at 60-70 revolutions per minute at an equivalent of 40W for 2 minutes. The study coordinator will oversee the workload and provide instruction to the participant as needed. Over the next 3 minutes, the study coordinator will increase the workload to either 45-55% or 65-75% of HRR (depending on randomization group). Blood pressure will be

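### The only nonparametric fallback named for the within-subject rest-to-exercise measures is the rank sum test, and the between-arm intensity comparison is mislabelled as paired

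*Combined protocol and SAP*

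**What the plan says.** Section V.A (Statistical and Data Analysis) describes the primary data for both aims as paired measurements before and after acute exercise, and continues: "As such, we will analyze the data using the two-sample, paired t-tests". The next sentence applies that one test to two contrasts: the overall change with exercise, and the difference between the moderate and higher intensity groups.

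Residual analyses are planned "to evaluate assumptions of common variance, normally distributed errors, etc". If the assumptions fail, "the nonparametric analogs will be used instead, such as the Wilcoxon rank sum test of the within-subject pre- vs. post-exercise measures".

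The sample size justification in the same section uses the label again, "A two sample paired t test design with an effect size of 1.25", for 15 AD subjects on high and 15 on moderate intensity. It gives 91% power at an effect size of 1.25, 75% at 1.00 and more than 95% at 1.50. Of the cited literature it says "This study produced an effect size of 2.07 based on the independent t test design", and it closes by relying on "the use of paired difference scores for the primary endpoint".

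On the design, Aim 1 says "subjects will undergo a single bout of moderate intensity (45-55% HRR) or higher intensity (65-75% HRR) exercise", and the Acute Exercise Protocol in section II.E has the coordinator "increase the workload to either 45-55% or 65-75% of HRR (depending on randomization group"). The FDG-PET imaging paragraph in section II.E plans paired t tests or linear mixed models for regional SUVR and names no rank-based method.

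**The concern.** The trial has two kinds of contrast. Rest versus exercise is within subject. Moderate versus higher intensity is between subjects, because each person does one bout at one randomized intensity. The plan gives both the same hybrid label, and then attaches to the within-subject contrast the rank test that belongs to the between-subject one.

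An analyst who followed the fallback sentence literally would discard the pairing on which the sample size justification relies. An analyst who saw the problem would have to choose another test after the residuals had been inspected. The stake is limited to the case where the fallback is triggered, but the plan lists both unequal variance and non-normality as triggers, and the cells are small (15 per diagnosis and intensity).

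**Working it through.** **Intensity contrast: which test gives the stated power?** Inputs from the sample size justification: 15 per arm; effect sizes d of 1.00, 1.25 and 1.50. Alpha is not stated; two-sided 0.05 is assumed.

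- Independent t test: 28 df, noncentrality d × √(15/2).
- Paired t test on 15 pairs: 14 df, noncentrality d × √15.

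| d | Plan | Independent, 15 vs 15 | 15 pairs |
|---|---|---|---|
| 1.00 | 75% | 75.3% | 94.9% |
| 1.25 | 91% | 91.0% | 99.4% |
| 1.50 | >95% | 97.7% | >99.9% |

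The plan's figures are those of the independent test. One-sided 0.05 gives 84.8% and 95.5% at 1.00 and 1.25, which does not match. The cited effect size also reproduces: pooled SD = √((0.27² + 0.68²)/2) = 0.517, and (4.25 − 3.18)/0.517 = 2.07.

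**Rest versus exercise: why the rank sum test misfires.** Its null distribution treats the two sets of values as independent. With the cited SDs (0.27 at rest, 0.68 with exercise), the variance of a within-subject difference is 0.27² + 0.68² − 2r(0.27)(0.68) = 0.535 − 0.367r. At r = 0 this is 0.535; at r = 0.5, 0.7 and 0.9 it is 0.352, 0.278 and 0.205. The signed-rank test uses the smaller variance; the rank sum test cannot.

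**Size of the loss.** Simulation of normal data with those SDs, two-sided 5%, exact critical values (n=15: U ≤ 64, W ≤ 25). The shift is in units of the pooled SD of 0.517. The correlation r, the shift and the normal shape are assumptions, because the plan gives none of them. Power is rank sum vs signed-rank:

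| r | Rank-sum type I error, n=15 | 0.5 SD, n=15 | 1.0 SD, n=15 |
|---|---|---|---|
| 0.5 | 2.7% | 22 vs 33% | 74 vs 87% |
| 0.7 | 1.7% | 20 vs 41% | 75 vs 93% |
| 0.9 | 0.9% | 19 vs 51% | 77 vs 98% |

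At n=30 (one whole diagnosis group) and a 1.0 SD shift, both tests have 97% power or more over these correlations. At 2.07 SD both have 100% at n=15. Signed-rank type I error stays at about 5%.

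Outside that range of r the direction changes: with the same SDs and n=15, rank-sum type I error is about 5.9% at r = 0 and 7.0% at r = −0.2.

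**The case against.** The best defence is that the sentence is compressed rather than wrong. Its governing commitment is to nonparametric analogues, the rank sum test is only an example, and the true analogue of a paired t test is signed-rank. The preceding text also covers the intensity groups, and the section uses change scores as outcomes elsewhere. Rank sum applied to change scores between intensity arms would be correct. In the same spirit, the hybrid t-test label may be loose wording for a two-sample test of paired differences.

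That reading is possible, but the sentence does not say it. It names the pre- and post-exercise measures, not change scores compared between arms. If the charitable reading is right, the within-subject contrast has no named fallback at all. The paired and mixed-model options under FDG-PET imaging concern regional SUVR and are parametric, so they do not fill the gap.

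It is also fair that the largest losses are at 0.5 SD, below any effect size in the plan (although 1.00 to 1.50 there refer to the intensity contrast), and that the cited SDs come from a different study with independent groups. With strongly skewed data and a shift of 1.0 SD or more, the two tests perform about equally. These points limit the size of the problem, not its existence.

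A reader might infer two stronger things. One is that the sample size was computed for the wrong test; the reproduced power figures rule this out. The other is that the fallback is harmless for false positives in all cases, or conversely that it inflates them. The documents support neither, because the direction depends on a correlation they do not give.

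**Conclusion.** Taken as written, the only example of a nonparametric fallback for the rest-to-exercise comparison is a test for independent samples, and the correct one is not named. The consequence is conditional on the fallback being triggered and the sentence being followed literally. Under positive correlation, which is plausible for repeat scans in the same person but is an assumption, the test is conservative and the cost is power: about 11 to 32 percentage points at 0.5 SD with 15 subjects (33 − 22 and 51 − 19), about 13 to 21 points at 1.0 SD (87 − 74 and 98 − 77), little at 1.0 SD with 30 subjects, and none at 2.07 SD. Near zero or negative correlation the test is not conservative.

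The paired label on the intensity comparison is a separate naming error with no effect on the stated power or sample size. Both points are of low severity and worth correcting because the correction is so cheap.

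**What to change.** Name the test for each contrast in section V.A:

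- Rest versus exercise within subjects: paired t test, with the Wilcoxon signed-rank test as fallback.
- Higher versus moderate intensity: independent two-sample t test on the rest-to-exercise change scores, with the Wilcoxon rank sum test on those change scores as fallback.

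Replace the hybrid two-sample/paired label accordingly, both in the analysis text and in the sample size justification. The cost is wording only: sample size, stated power and data collection are unchanged.

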**B. Subject Criteria (See Vulnerable Populations appendix, if applicable):**

1. Inclusion criteria:
  - Age 60 and older
  - Stable medication doses (>1month)
  - Post-menopausal
  - Diagnosis of either Nondemented (CDR 0) or Probable AD (CDR 0.5 or 1 only)
2. Exclusion criteria:
  - Inability to provide consent
  - Diagnosis of insulin-dependent (Type 1) Diabetes Mellitus
  - Recent ischemic heart disease (<2 years)
  - Diagnosis of an clinically significant chronic disease including CVD, other metabolic diseases (e.g., thyroid), cancer, HIV, or acquired immunodeficiency syndrome
  - Excluded from or unable to complete an MRI scan
  - Any Neurological disorders that have the potential to impair cognition or brain metabolism (e.g., Parkinson's disease, stroke defined as a clinical episode with neuroimaging evidence in an appropriate area to explain the symptoms).
  - Clinically significant depressive symptoms that may impair cognition, abnormalities in B12, RPR, or thyroid function that may impair cognition, use of psychoactive and investigational medications, and significant visual or auditory impairment
3. Withdrawal/Termination criteria: If the participant has a serious AE during the maximal cardiorespiratory fitness test (Visit 1) we will not have the participant return for the rest of the study. Participants are allowed to participate in other observational studies during their enrollment period but not interventional trials.

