**FDG-PET imaging:** FDG PET images will be obtained at a satellite location of the University of Kansas Hospital, the KU Cancer Center – Overland Park (KUCC-OP). The scanner is accredited by the American College of Radiology (ACR), and our physicists perform annual required testing by scanning an Esser PET phantom with 18F to assess SUV range, contrast resolution, spatial resolution, and uniformity. In addition to the ACR annual testing, the nuclear medicine department routinely performs quality control procedures on a daily, weekly, and quarterly basis. Frames are reconstructed to a single PET image in native space. Adverse events will be continuously monitored during the imaging session. The radiation dose from the two FDG PET scans will not exceed 2100 mrem. While this exceeds the amount obtained through normal background exposure, it is considered by Radiation Safety to be well below the risk levels acceptable in research and medical practice. PET images will be analyzed using custom software written for Statistical Parametric Mapping (SPM12). Pre- and post-intervention P images will be co-registered. A priori regions of interest masks from the Automated Anatomic Labeling series will be inverse warped to match native space images. The PET images will be standardized to the uptake value of the cerebellum and standardized uptake value ratios (SUVR) will be calculated from native-space ROIs as determined by MRI. Regional SUVR will be compared using paired t-tests or linear mixed models as appropriate.

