### **B. Primary Outcome:**

We expect that the global FDG-PET signal will decline following a single bout of acute exercise in AD and ND subjects, and that the drop will be greater from rest to higher intensity exercise compared to the drop from rest to moderate intensity exercise. We further expect that individuals who have a greater lactate AUC in the exercise compared to resting condition (i.e. greater “lactate response”) will have greater drop in cerebral glucose metabolism. This likely means that they are exercising closer to their lactate threshold – the point where blood lactate concentrations begin to increase exponentially. Thus, we expect to see a negative linear relationship between change in lactate AUC and change in cerebral glucose metabolism, and a positive relationship between change in lactate AUC and change in cognitive performance.

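### The plan claims intention-to-treat, but every stated test of the rest-to-exercise FDG change needs both scans, so the primary analysis is complete-case

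*Combined protocol and SAP*

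**What the plan says.** - **Endpoint.** The sample size justification in V.A relies on "the use of paired difference scores for the primary endpoint". V.B Primary Outcome puts the intensity hypothesis in the same terms, for the global FDG-PET signal: "the drop will be greater from rest to higher intensity exercise compared to the drop from rest to moderate intensity exercise". The two scans come from Visits 2 and 3, whose order is counterbalanced (II.A, II.E).
- **Tests.** V.A states: "As such, we will analyze the data using the two-sample, paired t-tests". Its nonparametric fallback works on within-subject measures, and its OLS models take change scores as the outcome.
- **Analysis principle.** V.A adds: "These measures will follow the intent-to-treat principals". It does not define the set.
- **Expected loss.** The sample size text says: "Accounting for a possible 10% attrition rate over the course of the study visits", and raises recruitment from 60 to 66.
- **Nearest alternative.** II.E, FDG-PET imaging: "Regional SUVR will be compared using paired t-tests or linear mixed models as appropriate". This concerns regional values and is not tied to the global outcome, to intention-to-treat or to missing scans.
- **A written exit.** After a serious adverse event at the Visit 1 fitness test, II.B.3 says "we will not have the participant return for the rest of the study".

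The documents contain no rule for a participant with one scan, no imputation, no missing-data assumption and no sensitivity analysis for loss.

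**The concern.** A difference score exists only when both scans are evaluable. Every stated test therefore deletes a randomised participant with one scan, and the result is a complete-case analysis under an intention-to-treat label.

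The randomised comparison is higher versus moderate intensity. Because visit order is counterbalanced, about half of the participants have the exercise scan first. If one of them leaves before the resting scan, the loss comes after exposure to the assigned intensity and could be related to it. The exercise scan is already on file, and the stated tests discard it. If such losses fall unevenly across the arms and track the response, the contrast is biased. Recruiting more people does not remove that.

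**Working it through.** **1. The plan's power figure.** Inputs from the sample size justification: 15 versus 15, effect size 1.25, stated power 91%. Alpha and sidedness are not stated, so two-sided 0.05 is assumed. The exact two-sample t test gives 91.0% at 1.25, 75.3% at 1.00 (stated 75%) and 97.7% at 1.50 (stated above 95%). The figures reproduce as a two-sample t test on complete change scores.

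**2. What 10% loss does to power.** 66 × 0.90 = 59.4 complete pairs, and 59.4 / 4 = 14.85 per diagnosis-by-intensity cell. At effect size 1.25 power is 91.0% (15 v 15), 90.0% (15 v 14) or 88.9% (14 v 14).

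**3. How many people have one scan.** 66 × 0.10 = 6.6, so at most 6 to 7. The 10% covers all visits. Visit 1 exits leave no scan. A missed Visit 4 MRI may leave neither scan scorable, since II.E takes the regions of interest from the MRI.

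**4. Possible bias.** This was simulated, because the documents give no data on who would be lost.
- Design: 33 per arm (both diagnoses pooled), half exercise-first, 10% expected loss, all after the first scan, and a true intensity difference of 1.25 SD of change. There were 1,500 trials per scenario.
- SDs: 0.27 (rest) and 0.68 (exercise), from the sample size text. They describe metabolic rate in separate groups and not SUVR, so they are illustrative. The rest-exercise correlation r is assumed to be 0.3, 0.5 or 0.73.
- Informative loss (assumed): more likely after a larger drop, log-odds slope 1 per SD, concentrated in the higher-intensity, exercise-first cell. That cell holds 33 / 2 = 16.5 people. Half of the loss there is 3.3 / 16.5 = 20% of the cell. All of the loss there is 6.6 / 16.5 = 40%.

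| Loss, SDs 0.27 / 0.68, r = 0.5 | Complete-case bias (SD of change) | All-scan model bias |
|---|---|---|
| Random | 0.00 | 0.00 |
| Half in that cell | 0.083 | 0.007 |
| All in that cell | 0.122 | 0.003 |

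Positive values mean shrinkage towards zero. Under random loss the standard error is 0.258 SD for complete cases and 0.252 SD for the model, so the gain is 0.006 / 0.258 = 2.3%. Against an SE of about 0.26 SD, the largest bias is 0.122 / 0.26 = 0.47 SE. At 16 per arm, near the size of the powered within-diagnosis contrast, complete-case bias was 0.06 and 0.11 SD. With an SE of about 0.37 SD that is 0.16 and 0.30 SE.

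**5. Does the model's advantage depend on the borrowed SDs?** Yes. The SD of change at r = 0.5 is √(0.27² + 0.68² − 2 × 0.5 × 0.27 × 0.68) = 0.593. The correlation of the exercise scan with the change is then (0.68² − 0.5 × 0.27 × 0.68) / (0.68 × 0.593) = 0.92. The observed scan almost stands in for the missing change. With equal SDs that correlation is √((1 − r) / 2), or 0.50 at r = 0.5 and 0.22 at r = 0.9. Re-run with equal SDs (assumed, r from 0.5 to 0.9):
- Loss depends on the drop itself: complete-case bias is about 0.08 to 0.12 SD, and the model keeps about 0.07 to 0.10 SD of it.
- Loss depends only on the observed exercise value: complete-case bias is 0.01 to 0.06 SD. The model's assumption holds, so it removes this.

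**The case against.** The strongest reply is that the gap is one of wording. Intention-to-treat may only mean analysis by assigned intensity, recruitment is already inflated for attrition, and II.E allows mixed models. The loss scenarios are also severe, removing 20% or 40% of one cell. Participants will already have completed a harder treadmill test, are not told their imaging results (III.F), and are paid once, at Visit 3 (III.G). Any resulting bias is towards the null.

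Much of this stands. Power is protected, the scenarios are assumptions, and the bias is modest even at the extreme. It does not settle the point. Analysis by assigned arm among completers still leaves out randomised people, and the mixed models in II.E are an optional alternative for regional values only.

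Three stronger readings are tempting, and the documents do not support them:
- **That 6 to 7 participants will have one scan.** This is an upper bound. Visit 1 exits have no scan, and no analysis of scans can recover them.
- **That a mixed model makes the bias negligible in general.** That result depends on the unequal borrowed SDs, or on loss driven by the observed scan.
- **That participants are randomised before Visit 1, so exits there breach intention-to-treat.** The documents do not say when intensity is assigned. The workload instruction in II.E needs it only at the exercise visit.

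**Conclusion.** The point holds as a mismatch between the stated principle and the stated tests. As written, the primary analysis is complete-case, and nothing in the plan says how a randomised participant with one evaluable scan is handled.

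The size is modest. Power stays at about 89 to 91% at effect size 1.25. Bias in the intensity contrast is zero under random loss and about 0 to 0.12 SD of change, towards the null, under informative loss concentrated in higher-intensity, exercise-first participants. That range rests on assumed loss mechanisms, assumed correlations and SDs that are not SUVR. The change is worth making because the claim should match the analysis and the remedy is cheap. There is no evidence here that the trial's conclusion is in danger.

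**What to change.** In V.A:
1. Make the primary analysis of global FDG change a likelihood-based repeated-measures (mixed) model of scan value on condition (rest or exercise), intensity arm and arm-by-condition. Use an unstructured 2×2 covariance and a small-sample degrees-of-freedom method such as Kenward-Roger. Include every randomised participant with at least one evaluable scan, and state this as the analysis set.
2. Keep the change-score t test as a sensitivity analysis labelled complete-case.
3. Report the number of one-scan participants by arm and visit order.

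The cost is revised wording and a few lines of code, with no added visits or participants. With complete data the arm-by-condition estimate equals the difference in mean change, so nothing is lost. The downside should be written into the plan: the model assumes missing-at-random given the observed scan. It removes bias from loss that depends on that scan, but little of it if loss depends on the unobserved change and the two scans have similar SDs. The precision gain is only about 0 to 3% of the standard error.

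### No diagnosis-adjusted higher-versus-moderate effect from all 60 participants is specified; power is given only for 15 v 15 AD participants, and the population of the between-intensity test is left open

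*Combined protocol and SAP*

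**What the plan says.** Aim 1 (section II, Study Objectives) and section V.B, Primary Outcome, predict a larger fall in brain glucose metabolism with higher than with moderate intensity, and cover both AD and ND participants. The design has four cells of 15: two diagnoses by two intensities.

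The sample size paragraph of section V.A bases its power on "a sample size of 15 AD subjects allocated to high intensity and 15 AD subjects allocated to moderate exercise". At that size the design "would yield an estimated power of 91% using a conservative estimated effect size of 1.25", while dropping the effect size "to 1.00 still provides 75% power", and "using a still conservative 1.50 for the effect size indicates >95% power". An equal number of ND participants is added without a power figure of its own.

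The analysis paragraph of the same section names t tests for the overall rest-to-exercise change and for the comparison between intensity groups. It does not say whether the second is done separately in AD and ND or across both. It then adds: "One further relationship will involve combining the results of the AD and ND subjects in a single model as described in our Aims". The test named for that combined model is given as "We will use OLS in this context to test for interactions between AD and ND subjects", with respect to the exercise response at the two intensities. Exploratory adjusted regressions on change scores are also planned, but their covariates are not listed.

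**The concern.** The higher-versus-moderate comparison is the only randomised comparison between people in this study. Both diagnosis groups are allocated to the same two intensities and the same direction of effect is predicted in each. The efficient estimate of the intensity effect therefore uses all 60 change scores, with diagnosis in the model. The plan does not specify that estimate.

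Two readings of the t test remain open, and each loses something. If it is run within diagnosis, each contrast rests on 30 participants, and its standard error is √2 times that of the contrast on 60. If it is an unadjusted comparison of 30 with 30, the difference between ND and AD that Aim 1 expects stays in the residual variance.

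The combined model does not close the gap as written. Where a model contains the interaction, what the intensity coefficient means depends on how diagnosis is coded. Under reference coding it is the effect in one diagnosis group. The averaged effect has to be asked for.

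**Working it through.** **Inputs.** From section V.A: 15 per cell, effect sizes 1.00, 1.25 and 1.50, stated power 75%, 91% and >95%. The documents give neither alpha nor sidedness; I assume two-sided 5%. Let d be the higher-minus-moderate difference in SDs of the change score within a diagnosis-by-intensity cell. Equal intensity effect and equal residual SD in AD and ND are assumed.

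**Formula.** With n per intensity arm, the noncentrality is d√(n/2) and power comes from the noncentral t distribution.

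**1. The plan's own figures (15 v 15, df = 28, critical t = 2.048).**
- d = 1.00: noncentrality 1.00 × √7.5 = 2.739, power 75.3% (stated 75%).
- d = 1.25: 1.25 × √7.5 = 3.423, power 91.0% (stated 91%).
- d = 1.50: 1.50 × √7.5 = 4.108, power 97.7% (stated >95%).

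All three agree. A true paired test with n = 15 would give 99.4% at d = 1.25, so the stated figures are for an independent 15 v 15 comparison.

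**2. Split against pooled with a diagnosis term (30 v 30, df = 60 − 3 = 57, critical t = 2.002).**

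| d | 15 v 15 | 30 v 30, adjusted |
|---|---|---|
| 0.8 | noncentrality 2.191, power 56.2% | noncentrality 3.098, power 86.1% |
| 1.00 | 2.739, 75.3% | 3.873, 96.8% |
| 1.25 | 3.423, 91.0% | 4.841, 99.7% |

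The standard error falls from √(2/15) = 0.365 SD to √(2/30) = 0.258 SD. The effect detectable with 90% power falls from 1.23 to 0.85 SD, and with 80% power from 1.06 to 0.74 SD. If 10% of the 60 were lost (27 v 27, df = 51), the pooled 90% figure would be 0.90 SD.

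**3. Unadjusted 30 v 30.** If mean change differs between ND and AD by g SD in a 1:1 mix, leaving diagnosis out multiplies the residual variance by about 1 + g²/4. Take d = 0.85, where the adjusted test has 90% power.
- g = 0.5: factor 1.0625, effective d = 0.85/√1.0625 = 0.825, power 88%.
- g = 1: factor 1.25, effective d = 0.85/√1.25 = 0.760, power 83%.

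The values of g are assumptions; the documents give none. The approximation somewhat overstates the loss when the four cells are exactly equal in size.

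**4. The test that is named for all 60.** The interaction (difference between the AD and ND intensity effects) has standard error √(4/15) = 0.516 SD on 56 df. Its power is 66%, 48% and 22% for differences of 1.25, 1.00 and 0.625 SD. The only combined test named is thus the least precise contrast the model offers.

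**5. Which effect sizes matter.** The source figure ("This study produced an effect size of 2.07 based on the independent t test design") compares exercise with rest: (4.25 − 3.18)/√((0.68² + 0.27²)/2) = 2.07. It is not a higher-versus-moderate difference, so values below 1 SD for the intensity contrast are plausible. That is where pooling gains most.

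**The case against.** The strongest reply is that the plan already has what is needed. Testing within diagnosis is nowhere stated: the t test is described without restriction, and section V.B frames the outcome for AD and ND together. A combined model is planned, and with its main effects it contains every term required for an averaged intensity effect. An AD-specific contrast is also a legitimate target, and its stated power is correct.

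Most of this stands. Within-diagnosis testing is an inference from the AD-only power calculation and from combining being introduced as a further step. The gap is one unspecified contrast and an unclear analysis population. It remains a gap, because neither reading yields the diagnosis-adjusted effect and the named test is a different one.

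A reader might go further in two ways that the documents do not support. The first is that half of the randomised participants go unused. On the within-diagnosis reading, 30 enter the AD contrast, 30 the ND contrast and all 60 the combined model; on the other reading all 60 enter the primary test. The second is that the study succeeds only if both diagnosis groups show an effect, so that joint power falls short of what is claimed. The plan sets no such criterion.

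Pooling also rests on similar intensity effects in the two groups. The plan intends to test that, so it cannot be presumed.

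**Conclusion.** The point holds as a cheap improvement in efficiency and clarity. The stated 75%, 91% and >95% are right for 15 v 15 under a two-sided 5% test.

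How much is lost depends on the reading. Within diagnosis, at d = 0.8 and 1.00 the plan gives up about 30 and 21 percentage points of power (86.1 − 56.2 and 96.8 − 75.3). At the planning value of 1.25 it gives up about 9 points (99.7 − 91.0). With an unadjusted pooled test, the loss at d = 0.85 is from 90% to 88% or 83% under the assumed gaps. The within-diagnosis comparison assumes the same intensity effect and residual SD in AD and ND. On either reading, under these assumptions, the adjusted model does better.

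**What to change.** In section V.A, state that the primary between-intensity test is the intensity effect averaged over diagnosis, from one linear model of change scores on all randomised participants with intensity and diagnosis as factors. Add the interaction to the same model to report AD- and ND-specific intensity estimates with confidence intervals, and keep the interaction test as secondary. State alpha and sidedness. In the sample size paragraph, give the power for this contrast, and retain the 15 v 15 figures as the power for the AD-specific estimate.

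The cost is wording only, with no extra participants, visits or measurements. The downside is one of interpretation: if the intensity effect differs by diagnosis, the primary estimate is an average over a 1:1 mix of AD and ND, which is why the diagnosis-specific estimates should be reported beside it.
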